Primary Endpoint Secondary Endpoints	
The primary endpoint of this study will be good handwashing practice defined as students who wash their hands with water and soap before eating assessed by structured handwashing observations.
 
The secondary endpoints are:
 
 Good handwashing practice defined as students who wash their hands with water and soap after using the toilet assessed by structured handwashing observation Self-reported handwashing practice answered for two critical events; before eating and after using the toilet, on a Likert scale ranging from almost never to almost always. The well-being of students assessed by KINDL tool Number of total coliforms and E.coli colony-forming units (CFUs) per hand before handwashing. Hygiene-related health outcomes and absenteeism incidence. The health outcomes will be reassessed with local experts in the country to assure feasibility before the start of the intervention.
Study Design	
Overall project: Multi-center cluster-randomized controlled trial (cRCT) design.
 
Module 1-3 will be repeated three times within the cRCT at baseline, three months post-intervention and at endline. Module 4 data collection will take place in both study arms longitudinally starting after the intervention has been implemented. Module 5 will be a self-reported survey administered for the parents of the students included in the study at baseline in Palestine. Module 6 and 7 are qualitative focus group discussions (FGDs) and interviews and will take place after the second round of data collection in Modules 1-3.

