Inclusion/Exclusion Criteria	
Study participants are primary school students aged 10-12 years attending eligible schools that were selected to be included in this study.
 
Inclusion criteria Modules 1-4: Schools were selected based on accessibility for the study teams, not having a water source directly connected to the building of the school, having primary grades (5th-7th), having ≤ 7000 students and being impacted by conflict.
 
50 students will be randomly selected from one or two classes in the included schools and they must fulfil all the inclusion criteria:
 
 - Age between 10-12 years or attending grades 5th-7th - Students, male and female, who are in classes close to where the handwashing stations (Gravit'eau) will be positioned in the school (in Nigeria) - Students must be in the same school for the course of the study (1 year). 
Exclusion criteria Modules 1-4: students must not fulfil any of the following exclusion criteria:
 
 - Refusal to participate by not providing signed consent forms or oral assent - having any medical condition that prevents them from washing their hands - having unexplained intermittent attendance in school (school teachers will be consulted and school's absenteeism records will be checked for that) - will not be at the same school for the course of the study (1 year)

- not meeting the inclusion criteria

Inclusion criteria Module 5:

- Students of the classes included in the study in each included school in Palestine

Exclusion criteria Module 5: Refusal to participate by the student or his/her parents

Inclusion criteria Module 6:

For students:

- Students of the intervention schools
- Students from the 50-student sample selected in each included school

For teachers:

- Aged \geq 18 years old
- Permanent employees in the school
- Teaching one of the classes included in the intervention

Exclusion criteria Module 6: Not providing signed consent form and/or oral assent

Inclusion criteria Module 7:

- The participant needs to be:
 - a) a stakeholder within the community, state, region or country of the intervention whose position is related in any way to WASH in schools
 - b) working in one of the intervention schools. They can be teachers, hygiene technicians or in a leading position of the school.
 - c) Minimum age of 18 years

Exclusion criteria Module 7: Refusals to participate

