
Measurements and Procedures
	
Different methods across modules will be used to achieve the objectives of this project. These modules will include qualitative and quantitative data approaches in order to enable a triangulation of the overall project results. The following modules will be used in the cRCT and the overall project: (i) Module 1: A combined RANAS and wellbeing survey, (ii) Module 2: Structured handwashing observations, (iii) Module 3: Microbiological analysis of hand rinse samples, (iv) Module 4: Diary approach for pre-defined health outcomes and absenteeism incidence, (v) Module 5: personal, physical, and social contextual factor survey, (vi) Module 6:FGDs and (vii) Module 7: Key informant interviews (KII).
 
Endpoints of Modules 1-3 will be assessed at baseline, at follow-up and endline of the cRCT. Module 4 will be used to collect data longitudinally over the course of 12 months. Module 5 will be assessed at baseline and only in Palestine, Module 6 and 7 will be used in the middle of the intervention phase in the intervention groups.

Number of Participants with Rationale (if no Power Analysis conducted)
	
The sample size calculation yielded that 13 schools are needed per arm with 50 students per school. With political instability and other factors which might lead to a loss of follow-up, we have 7 schools as backup schools. This will lead to 26 schools in total with a total number of 1300 students. The number of students participating in different modules will differ due to the capacity limitation of assessing the 50 students included in each school. For module 1, only 25 students of the 50 students included in the study in each school. For module 2, the 50 students included in the study in each school will be targeted for assessment using this module. For Module 3, 12 students out of the 25 randomly selected students to be targeted with RANAS and well-being survey will be targeted for assessment using this module.

	
Module 4 follows the sample size calculation of the cRCT design, hence 50 students from each of the 26 schools will be monitored. For Module 5, all students in the included classes in each school in Palestine will be delivered a survey to be self-reported by their parents. For Module 6, 10 FGDs (including students) and 5 FGDs (including teachers) will be administered and for Module 7, 10-20 interviews.

Study Duration	14 months

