Study Schedule	
For Nigeria: May 2023 of First-Participant-In July 2024 of Last-Participant-Out
 
For Palestine: March 2023 of First-Participant-In May 2024 of Last-Participant-Out

Investigator(s)	
[name]. [name] Swiss Tropical and Public Health Institute [name] [contact] [contact]
 
PhD candidate (research assistant) under supervision of [name]. [name]: [name] Swiss Tropical and Public Health Institute [name], Switzerland [contact]
 
[name] Terre des hommes Nigeria [name] [contact], [name] [contact]
 
[name] Project coordinator Cesvi Palestine [name] [name] [contact]
 
[name] Junior Programme Officer Skat Foundation [name] [contact] [contact]

Study Centre(s)	Nigeria and Palestine
Statistical Analysis incl. Power Analysis	The number of clusters (schools) and students per school were calculated using the software R with a power simulation of 80% developed by [name]. The Intraclass Correlation Coefficient (ICC) was assumed at 0.2. The simulation assumed a prevalence of handwashing occurrence before eating during the time of observation (3 hours) taking place over one day of 20% in control vs 45% in intervention schools after 1 year from the

	
baseline. Based on this assumption, 13 schools are needed per arm with 50 students per school.
 
The baseline data will be reported descriptively. The imbalance at baseline between trial arms will be assessed in terms of clinical importance rather than in terms of statistical significance. The intervention effect will be estimated with logistic mixed effect regression to adjust for potential correlation within schools. For the primary analysis, the model will include only the outcome (handwashing occurrence before eating during the time of observation (3 hours) taking place over one day and assessed at the endline) and the intervention as a predictor and school as a random effect. Further analyses will include known confounders and variables imbalanced at baseline. All analyses will use the available case population. No imputation of missing data will be done because loss to follow-up is usually small to moderate in school-based studies.

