3.1.3 Secondary objectives

Additionally to the primary objective, the H4H project aims to address the following secondary objectives and research questions:

1) Evaluate the effects of the H4H MCI on the well-being of primary school students in Nigeria and Palestine

RQ 1.1 Can a quantifiable change in well-being be detected due to the intervention?

2) Assess the effect of the H4H MCI package on hygiene-related risks, attitudes, norms, abilities and self-regulation (RANAS) behavioural factors of primary school students

RQ 2.1: Can the H4H intervention package be associated with a change in hygiene-related RANAS behavioural factors of primary school students?

RQ 2.2: Which factors promote the uptake of the intervention?

3) Explore the associations of personal, physical and social contextual factors with hand hygiene and well-being of primary school students in Palestine

RQ 4.1 Which factors related to personal, social or physical contexts are independently or jointly associated with hand hygiene and well-being?

4) Explore the perceived impacts of the H4H MCI package on the health and well-being of primary school students

RQ 4.1 What are the students' and teachers' perceived impacts of the H4H MCI on their hand hygiene, health and other issues?

RQ 4.2 What are the students' and teachers' perceived obstacles and challenges for scaling up the H4H MCI in the schools?

RQ 4.3 What are the proposed solutions for addressing these challenges?

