The study design will be baseline cross-sectional. This objective will be fulfilled through the baseline assessment conducted before randomising the recruited schools in Palestine into the two arms of the study. The assessment will be carried out through a survey that is self-reported by the parents of the students in the selected classes for the study. The survey will include questions related to the availability of hygiene services at the household level, evaluation of parents' hygiene knowledge and behaviour, and assessment of their child's hygiene behaviour as reported by them.

Module 6: Focus Group Discussions: The FGD is a rapid and resource-efficient method of gathering information since all the target participants and the researcher are readily available at the same study site (Mack *et al.* 2005; Nyumba *et al.* 2018). There is no need to collect participants from different environments and prepare them in advance, rather, they will be met in their usual studying environment which also helps not to introduce their expectations and biases, including strategic group bias (Nyumba *et al.* 2018). Also, the concentrated nature of the FGD avails a large quantity of data in much less time usually needed to collect an equivalent number of interviews (Nyumba *et al.* 2018).

10 gender-separated FGDs will take place in the included schools in the intervention arm; 5 FGDs for each gender in autumn 2023. However, the saturation factor⁶ will be considered when conducting the discussions in the field. Each group will include students of the same age of the age group target (10-12) to avoid any domination of older students if the groups include different age groups. Using separate groups for boys and girls will help ensure meaningful feedback since children may feel shy speaking in front of each other and usually there is an increase in teasing among children at the age of 10 (Dzino-Silajdzic 2018). It is important for them to feel comfortable speaking their minds freely and not feel shy, embarrassed or worried someone will make fun of them (Dzino-Silajdzic 2018). Each FGD will be composed of 5-8 selected students. The selection of the students will be consulted with the school administration, however, selected students need to represent each participating class in the intervention arm of the trial.

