5.2 Inclusion criteria

Study participants will be primary school students of schools selected to be included in this study. Schools were selected based on accessibility for the study teams, not having a water source directly connected to the building of the school, having \leq 7000 students. 50 students within the age of 10-12 years old from one or two classes (depending on the number of students in classes) of the 5th-7th grades will be included in the study from each included school. However, due to the large size of the schools and high number of classes in Nigeria, the 50 students will be selected from two classes of the 5th-7th grades close to where the handwashing stations (Gravit'eau) will be positioned. The 50 selected students will be targeted with the handwashing observation (Module 2) and followed for their hygiene-related health outcomes and absenteeism during the course of the study (Module 4), while 25 of them will be targeted with RANAS and well-being survey (Module 1) and 12 of them will be targeted with collecting their hand-rinse samples (Module 3). Students in the selected classes in each school will be delivered a survey to be self-reported by one of their parents about contextual factors that could affect hygiene practice of students (Module 5 in Palestine only).

Inclusion criteria Modules 1-4: students must fulfil all the inclusion criteria:

- Primary school students aged 10-12 years attending included schools
- Students must be in the same school for the course of the study (1 year).

Inclusion criteria Module 5: students must fulfil all the inclusion criteria:

- Students of the classes included in the study in each included school in Palestine

Inclusion criteria Module 6:

- Students of the intervention schools
- Students need to represent each included class in the intervention.

The teachers invited to participate in the FGDs should be

- Aged \geq 18 years old
- Permanent employees in the school
- Teaching one of the classes included in the intervention

Inclusion criteria Module 7:

- The participant needs to be:
 - a) a stakeholder within the community, state, or region of the intervention whose position is related in any way to WASH in schools
 - b) working in one of the intervention schools. They can be hygiene technicians, teachers, school's principal, or in a leading position in the school.
- Aged \geq 18 years old

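### Student focus groups recruit from the primary-outcome sample, in the intervention arm only and before endline: a small one-sided bias risk that rewording can largely avoid

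*Combined protocol and SAP*

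**What the plan says.** - **Who attends.** The Synopsis (inclusion criteria, Module 6) asks for pupils of the intervention schools who are "Students from the 50-student sample selected in each included school". Section 5.2 does not name the sample; it asks for intervention-school pupils and adds: "Students need to represent each included class in the intervention". Section 5.1 has the same class rule and leaves the choice of pupils to consultation with the school administration.
- **How many.** Section 4, Module 6: "10 gender-separated FGDs will take place in the included schools in the intervention arm; 5 FGDs for each gender in autumn 2023", and "Each FGD will be composed of 5-8 selected students". Saturation may alter the number of groups.
- **Which arm, and when.** The Synopsis says "Module 6 and 7 will be used in the middle of the intervention phase in the intervention groups" and that these modules "will take place after the second round of data collection in Modules 1-3".
- **Topic.** Section 3.1.3 asks: "What are the students' and teachers' perceived impacts of the H4H MCI on their hand hygiene, health and other issues". Its other questions concern obstacles to scale-up and proposed solutions. Section 4.4 caps a session at one hour.
- **Primary outcome.** All 50 pupils per school are observed (section 4, Module 2). The primary model uses handwashing before eating, "taking place over one day and assessed at the endline" (Synopsis, Statistical Analysis).
- **Safeguards.** Section 4.3 places the survey on the day after the observation, because survey questions might themselves improve handwashing. It has no equivalent for Module 6, and section 6.3 plans no analysis that takes attendance into account.

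**The concern.** Section 4 lists the package as handwashing station, behaviour change, capacity development and management support. A focus group is none of these and would not come with a roll-out. The survey and the hand-rinse samples also touch outcome pupils, but in both arms, so any prompting from them is roughly balanced. The focus group reaches outcome pupils in one arm only. If talking about handwashing with study staff changes behaviour at all, the change enters the estimated effect of the package, most plausibly in its favour, and a larger sample would not remove it. Nor can it be cleanly removed in the analysis, because attendees are not chosen at random.

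The differing eligibility rules are a practical problem in themselves: a field team cannot tell whether it must use the 50 or may use any pupil in the participating classes.

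**Working it through.** **1. The plan's own figure.** Inputs from section 6.2: 20% v 45%, ICC 0.2, 50 pupils per school, 80% power, 95% confidence (taken as two-sided 5%).
- Design effect = 1 + (50 − 1) × 0.2 = 10.8.
- The standard two-proportion formula gives 54 independent pupils per arm, or 62 with continuity correction. Schools per arm = 54 × 10.8 / 50 = 11.7, or 62 × 10.8 / 50 = 13.4.
- A simulation (20,000 runs, beta-binomial schools, t-test on school proportions) gives 78.1% power with 12 schools per arm and 81.8% with 13.

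So 13 per arm reproduces, and the planned difference is 25 points.

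**2. Order of events.** Section 4.3 repeats Modules 1-3 at three and nine months after the intervention, so rounds 2 and 3 are about 9 − 3 = 6 months apart. The groups fall between them, in autumn 2023. Last participant out is May 2024 (Palestine) or July 2024 (Nigeria).

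**3. Exposure.** Attendees = 10 × 5 to 10 × 8 = 50 to 80. The denominator is uncertain. The Synopsis gives 26 schools in total, so 13 × 50 = 650 intervention pupils. Section 4 gives 26 per country, so 26 × 50 = 1,300.

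**4. Direct shift in the arm difference.** Shift = share of attendees × change among attendees; control schools do not move. The changes are assumptions, since the documents give none.

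| Attendees / intervention pupils | Share | 10-point change | 25-point change | Ceiling |
|---|---|---|---|---|
| 50 / 650 | 7.7% | 0.8 | 1.9 | 4.2 |
| 80 / 650 | 12.3% | 1.2 | 3.1 | 6.8 |
| 50 / 1,300 | 3.8% | 0.4 | 1.0 | 2.1 |
| 80 / 1,300 | 6.2% | 0.6 | 1.5 | 3.4 |

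The 25-point column is generous: it credits one discussion with as much as the whole package is planned to achieve. The ceiling has every non-washing attendee switch when 45% already wash (share × 55). It is a bound, not a forecast. Spread to classmates is not counted.

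The table takes 10 groups as the total, as the text reads. With 10 groups per country and 26 schools per country, the shares are 100/1,300 = 7.7% and 160/1,300 = 12.3%, as in the first two rows. Ten per country against 13 intervention schools overall would double those rows, but no section states that.

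**5. Effect on a false positive.** With 20% in both arms, SE = √(2 × 0.2 × 0.8 × 10.8 / 650) = 7.29 points, or 5.16 points with 1,300 per arm. Rejection probability = 1 − Φ(1.96 − shift/SE) + Φ(−1.96 − shift/SE). A 10-point change among attendees moves the 5% level to 5.1-5.3%; a 25-point change moves it to 5.4-7.1%.

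**6. Pupils available outside the 50.**
- Nigeria: classes average 51-101 (section 3.2) and section 5.2 uses two, so about 2 × 51 − 50 = 52 to 2 × 101 − 50 = 152 remain. If one class were used, as section 4 allows, 1 to 51 remain.
- Palestine: classes of about 30 (section 3.2), so 2 × 30 − 50 = 10 remain. Some of these may be ineligible or have refused, and groups must be single-sex and of one age.

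**The case against.** The case against is substantial. The groups ask about experience, obstacles and solutions; they do not promote handwashing. Intervention pupils already receive behaviour-change activities, and half the sample is surveyed on handwashing at baseline and at three months, so one further discussion may add little. The reasoning in section 4.3 concerns questions put just before an observation, whereas here months intervene. Qualitative work during the intervention is a deliberate choice and belongs in the intervention arm.

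Most of this stands, and it is why the point is minor. It does not answer the asymmetry: the survey runs in both arms, the focus group in one. The purpose of the groups does not require that attendees be outcome pupils.

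A reader might infer three stronger things that the documents do not support:
- **That the contact can only raise handwashing.** Neither direction nor persistence is established. A rise is the most plausible effect, if there is one.
- **That the groups undo the concealment in section 4.3.** That section keeps pupils unaware of being observed, not unaware that the project concerns handwashing. A discussion of perceived impacts need not disclose the observation.
- **That section 5.2 already keeps the 50 out.** It is silent on the sample. Excluding them would be a new criterion.

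**Conclusion.** The point holds as a cheap improvement. As the Synopsis stands, 50-80 outcome pupils in one arm receive a hand-hygiene research contact before endline, and no safeguard or analysis addresses it. At an assumed 10-point change the direct shift is about 0.4-1.2 points of the planned 25. A reader might conclude that the groups could account for a positive trial, but even the ceiling in the table is 6.8 points. The figures assume 10 groups in total, no spread between pupils and no fading by endline; spread would raise them and fading would lower them. They are on the scale of proportions, whereas the primary model reports an odds ratio. The difference between the Synopsis and sections 5.1 and 5.2 needs resolving whatever view is taken of the bias.

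**What to change.** Give the Synopsis and sections 4 (Module 6), 5.1 and 5.2 one eligibility rule. Student focus groups recruit from the participating classes but outside the 50-pupil sample, where class size allows. Where it does not, that school's student groups take place after its endline observation. The first rule should serve Nigeria. The second would probably apply to most Palestinian student groups. State also whether the 10 groups are overall or per country.

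**Cost.** Protocol wording, with no change to the 13 schools of 50 per arm. The Palestinian student groups lose the mid-intervention timing set in the Synopsis, and with it their mid-course feedback.

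**What remains.** Recruiting classmates removes direct exposure of outcome pupils but not spread between pupils; holding the groups after endline removes both. Teacher groups and school-staff interviews in the intervention arm are untouched. If any outcome pupil does attend, record it by participant ID and report a sensitivity analysis without attendees, noting that they were not randomly chosen.

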2 BACKGROUND INFORMATION

2.1 Global public health relevance of water and hygiene

Water insecurity has been a primary underlying determinant of global health disparities (Stevenson *et al.* 2012). In recognition of the importance of achieving universal access to safe water and hygiene services, one of the 17 Sustainable Development Goals (SDGs) established by the United Nations in 2015 is dedicated to “ensure availability and sustainable management of water and sanitation for all” (SDG 6) (UN 2015). Improving access to water and hygiene contributes to enhancing several essential aspects of life and achieving other SDGs (UN 2006), such as contributing to ending poverty (SDG 1) and hunger (SDG 2), promoting health and well-being for all at all ages (SDG 3) and empowering women (SDG 5) (UN 2015).

Despite considerable progress in increasing access to safe water and sanitation, billions of people –primarily located in low- and middle-income countries (LMICs) (Guardiola *et al.* 2014; Kangmennaang and Elliott 2021) – still lack access to essential water and hygiene services required for a healthy life and well-being (WHO and UNICEF 2019). More specifically, a third of the world’s population does not have access to safe drinking water and 40% lack access to basic handwashing facilities with water and soap (WHO and UNICEF 2019). Consequently, billions of people are exposed to increased risk of water and hygiene-related diseases, with an estimated 2 million people, predominantly children, dying each year from diarrheal diseases alone (WHO and UNICEF 2019). A problem that is aggravated among children under five in LMICs by the exposure to drought that is likely to increase due to climate change (Wang *et al.* 2022).

